6.2.3 Pharmacokinetics (if applicable)

Not applicable

6.2.4 Biomarkers (if applicable)

Not applicable

6.3.1 Study Schedule

The duration of the pre-implementation phase is 6 months. During this time, we will collect observational data through the environmental scan, and data on practice characteristics via the EMR.

The duration of the implementation phase is 12 months. The intervention includes site visits by a practice facilitator. It is estimated that facilitators will conduct a minimum of 13 sites visits over the 12 month intervention period. In addition to the site visits, patients and clinical and non-clinical staff will participate in two study visits over the course of 12 months: baseline and 12 months

The estimated time for each study visit is outlined below:

Patients:

QI improvement interviews at 3 and 6 months: 15 min

Consent/Baseline visit: 30 minutes

Final study visit (survey and exit interviews) at 12 months: 75 minutes

Staff:

Consent: 10 minutes

Baseline: 20 minutes

Final study visit at 12 months: 60 minutes

The study visits are not linked. Staff will be consented at both baseline and final study visit.

6.3.2 Informed Consent

Both patients and clinical/nonclinical staff will provide informed consent to participate in this study. The New York University IRB will approve the protocol and consent.

Clinical/nonclinical staff Survey Consenting Process: Due to COVID-19 regulations, staff will complete the consent form and the baseline surveys remotely via RedCap. A RedCap link will be sent to a general email distribution list with information about the study and staff interested in participating will click on the link, provide informed consent and complete the baseline, and/or the 12-month surveys anonymously.

After clicking on the link, potential participants will read the 'consent statement' which includes PI name, brief study purpose, details on voluntary participation, ability to stop at any time without explanation and further, that such action will in no way affect their relationship with the primary care practice, confidentiality (anonymous survey), risks/benefits, etc. The email will emphasize that participation is voluntary and refusal to participate will not affect employment or job performance evaluation. They will then be given the option of whether they choose to participate. If they choose to participate, they will proceed to the survey, otherwise, participants will terminate the survey.

All participants will have the capacity to give consent. Comprehension will be assumed when participants read and accept the terms of consent statement prior to initiating the survey. Debriefing procedures will not be necessary.

For the clinical/nonclinical staff only clicking on the “proceed to the survey” button, will be the subject’s documentation of consent to participate in the study. Staff will be consented at both baseline and final study visit and consent/surveys will not be linked as the surveys are anonymous.

Clinical/nonclinical staff Exit Interview Consenting Process: A random sample of 30 clinical/nonclinical across all 10 practices will complete an exit interview where they will be queried about their experiences with ALTA and the PF intervention (if applicable) over the past 12 months and recommendations for improvements. This visit should take 30 minutes.

Participation is voluntarily and those interested in participating will be encouraged to sign and date a consent form. The interviews will be completed in-person or virtually to accommodate to the current COVID-19 situation. The interview method (face-to-face face vs. virtual) will be determined at the discretion and preference of the participants, while following practices and NYU institutional regulations for COVID-19. Invitation to participate will be random. A RedCap link will be sent to a general email distribution list with information about the exit interview and staff interested in participating will click on the link to provide informed consent. An RA will then proceed to arrange a meeting with staff to review the consent form and answer questions staff may have. Audio recording will be obtained and after the interview is recorded it will be transcribed and identifier removed to protect the subject.

Patients: Patient consent will be conducted during an in-person meeting with a RA in a private place at the practice. During the meeting the RA will give a fuller description of the study to the participant in clear, easy to-understand language, emphasizing the points made during the initial telephone call/letter/Epic invitation. All patients will be told that their responses are anonymous and confidential, that they may refuse to participate in the project or withdraw at any time without explanation, and further, that such action will in no way affect their future interactions with their PCP. If the patient remains interested in participating, they will be provided with a copy of the consent form to read; if the patient asks for help or evidences a problem in reading the consent due to literacy issues, the RA will read and explain the consent him/her. Patients will be asked to repeat back to the salient points of the consent form to make sure that they understand the study they are agreeing to participate in. Patients who exhibit any cognitive deficits will not be eligible to participate in this study. If the patient desires to participate, s/he will sign, and the RA will co-sign. Participants will receive a copy of the signed informed consent. A second copy will be stored in a secure, locked filing cabinet in a dedicated room. We are also submitting a waiver of documentation consent in order to obtain verbal consent as an option for patients. We are requesting verbal consent to assist participants who are uncomfortable using redcap on their phones the opportunity to verbally consent. As we continue using traditional recruitment methods virtually (i.e., calling patients), we’ve repeatedly encountered challenges with obtaining electronic consent from older patients. While we guide them through the process of opening and submitting the REDCap form, many have expressed frustration with the technology. Adding a verbal consent option would significantly reduce this barrier and improve patients’ willingness to complete brief virtual surveys.

We are providing the options for both written and verbal informed consent. The consent form will be reviewed with all patients by a research assistant and patients can choose to provide consent in written form or verbal form and the study team will document as such in REDCap. In anticipation of crossover from the control to the intervention group, we are using a single consent form for the evaluation.

Due to COVID-19 and to keep the safety of both our research team and research subjects, we are slightly modifying our consenting strategy to maintain our original plan of doing in-person consenting strategies as well as to permanently include collecting virtual consent (e.g., via telephone, using RedCap), as follows. Once the participant agrees to participate in the study, a trained RA will schedule a time with eligible interested participants to go over the written consent via telephone. RAs will email or mail a copy of the consent to participants in preparation for the telephone consent. After going over the written consent via telephone, RAs will also send the consent via an IRB approved RedCap link where the participant has the opportunity to read the consent and sign it electronically as well as to confirm that they read and understood the consent. Once the participant has signed the consent form, the RA will print out the signature page, sign it and mail it back to the participant. A copy of the signed consent form will be kept securely on file in the participant's study folder. Alternatively, participants will have the option to use finger signature in RedCap and mail the signed page of the consent back to the RA. The RA will then sign and mail the consent back to the participant. A copy of the signed consent will be kept securely on file in the participant's study folder. RAs will also document on RedCap the time and date of the telephone consent and note that the consent process was done via telephone.

The RAs on the project will have previous experience working on intervention trials and as part of this work have obtained informed consent from demographically diverse participants. Further, the RAs will be experienced with consenting Spanish-speaking participants. If the participants speak Spanish, they will receive an IRB approved Spanish translated Consent form. The Spanish consent form will be explained by a Spanish-speaking RA. A modification will be submitted that contains only translated research materials, including the informed consent documents.

6.3.3 Screening

Trained RAs will be responsible for screening potentially eligible participants from the practices. Once a potentially eligible patient is identified for this study, they will be screened using a standardized form that outlines the study's inclusion and exclusion criteria. Study staff will obtain verbal consent prior to beginning the eligibility screening. Only participants that meet all eligibility criteria will provide written informed consent.

6.3.4 Recruitment, Enrollment and Retention

Practice clinical and non-clinical staff will be recruited through study team attendance at the monthly staff meetings, email communications that describe the project including the overarching goals and what is expected of participants, and in-person or virtual meetings with the practices.

We will recruit approximately 500 patients across the practices who meet the following eligibility criteria (described above). Several strategies will be used to maximize the number

of eligible patient participants recruited per practice as described below. Signed informed consent will be obtained from participants who meet the study eligibility criteria.

Since this is a clinic wide initiative, we are broadening our eligibility criteria to include patients of all race and ethnicities, and not be exclusive to Latinx patients (this is also reflected in the change to our project name). We will still recruit a random sample of 70 patients per clinic that receive care in the 10 safety-net practices to participate in the surveys to assess our tertiary outcomes. Of this sample, 30 will be randomly selected to participate in an exit interview. Patients will be randomly selected from a list of patients who receive care in the clinics and have been exposed to the ALTA project. The same recruitment strategies will be employed to recruit 300 patients who receive care in the clinics and met eligibility for ALTA but did not ultimately participate in the project. All patients will provide written informed consent prior to participating in the study.

Method 1: Recruiting Using EHRs through EPIC: We will use EPIC to identify potentially eligible patients seen in the practices, based on DRG codes indicating presence of hypertension. Each month we will create a roster of potentially eligible patients through a review of the EHR-embedded HTN registry for each treating physician in the practice. Primary care providers will be asked to review the list of their eligible patients, and then asked permission to enroll the patients in this study. Lists of patients deemed appropriate (i.e., "yes") by the physician will be generated. Following permission from practice treating physicians to recruit their patients to the study, patients will be approached and screened using the following process: (a) A letter signed by the treating physician and [name] will be sent to the treating physician's patients notifying them of the study, and informing that an NYULH clinical staff person will contact them to explore their willingness to consider participation, or that their patients can call directly to the study staff to ask about the study. (b) Study staff will call patients who agree to be contacted, describe the study and, if the patient expresses an interest, conduct preliminary screening by telephone. Verbal consent is obtained by study staff prior to eligibility screening. (c) For potentially eligible patients with active MyChart accounts that have agreed to be contacted for research and indicate yes under the "recruiting ok?" option on EPIC, study staff will send the already IRB approved email script via Epic. The patient will receive the message via MyChart and it will automatically be noted on their EHR as an encounter message. (d) Written informed consent will be obtained with subsequent in-person or virtual visit for eligible participants to accommodate to the current COVID-19 situation. The consenting method (face-to-face face vs. virtual) will be determined at the discretion and preference of the participants at the time of the telephone screening, while following practices and NYU institutional regulations for COVID-19. An IRB-approved waiver of authorization will be obtained prior to searching the EHR.

Method 2: Participant self-referral through EPIC EHR MyChart alerts: We will provide the NYULH Epic Research Integration team with a list of potentially eligible patients provided to us by NYULH DataCore services through an IRB-approved waiver of authorization. The Epic team will create weekly reports on upcoming appointments from this potentially eligible patient's list, and will send these patients an alert notification two weeks prior to these

appointments. These alerts will inform patients to check MyChart electronic record for a new message. A modification will be submitted with the alert text prior to starting the study.

We will provide a NYULH Epic Research Integration team with an IRB-approved patient-facing script to be posted in the Epic electronic health record patient portal (MyChart) with a brief study description and encouragement to discuss the study with their treating physician on their next appointment. After this encounter, the Epic Research Integration team will send a second alert to potential participants after their medical appointment for them to check MyChart for another IRB-approved message reminding patients to contact study staff for any questions or to express their interest to participate. At this point, study recruitment proceeds as per protocol: (a) study staff describe the study and, if the patient expresses an interest, conduct preliminary screening by telephone. Verbal consent is obtained by study staff prior to eligibility screening. (b) Written informed consent will be obtained with subsequent in-person or virtual visit for eligible participants to accommodate to the current COVID-19 situation. A modification will be submitted with the alert text prior to starting the study.

Method 3: Self-referral from advertisements placed in the practices: IRB-approved fliers and brochures containing an overview of the study will be created and displayed in the clinical practice setting for those who may be interested. Interested patients will be provided with the phone number of the study staff that they may call to obtain additional information about the study. Those participants contacting the study office will be provided a brief description of the goals of the study and what their participation would entail. Those who remain interested will be screened to assure that they meet eligibility criteria and schedule an informed consent in-person or virtual visit. We will contact the patients' healthcare provider/agent to determine if their patient is fit to participate in the study. A modification will be submitted with flyers prior to starting the study.

Method 4: Physician referral: During the provision of routine ambulatory care, physicians will identify potentially eligible participants and ask about their interest in a study that proposes to examine how patient and providers talk about taking medications. Interested patients will be advised to contact the study by telephone to discuss possible enrollment. Interested patients will be provided with the phone number of the investigators that they may call to obtain additional information about the study. Those participants contacting the study office will be provided a brief description of the goals of the study and what their participation would entail. Those who remain interested will be screened to assure that they meet eligibility criteria and will be scheduled to complete the informed consent in-person or virtual visit.

Method 5: The study team will also conduct in-service in-person or virtual visits with the study sites prior to patient enrollment and every 3 months thereafter to explain the study rationale, its significance and procedures. At this time, clinic staff will be given a postcard (either digital or paper copy) that lists eligibility criteria and contact information for the RAs. During these in-person or virtual visits, personnel from each site with access to hypertension registries (nurses or staff participating in ALTA) will be assigned, with help from leadership,

to send a monthly roster list with potential eligible participants scheduled to see their PCP in the following month.

We will use several strategies to retain practices and participants while they are enrolled in the trial. These include: (1) Signed memorandum of understanding (MOU): We have found that this formal agreement ensures that the sites understand the purpose of the study and their roles and responsibilities for participation, which increases the likelihood of retention. The MOU also highlights the benefits of participating in the project. All sites will be asked to sign this agreement as part of the recruitment and enrollment process. (2) Identify a practice champion or key contact to act as a liaison: This is also crucially important to ensure fidelity to the implementation of the ALTA intervention into the clinic workflow. (3) Offer monetary incentives for participation. For patients, this includes offering appropriate incentives, time to complete study visits, periodic phone calls, and transportation to the sites (total incentive: \$70: \$25 for each of the two study visits (baseline and 12 months; \$20 for the exit interview, if selected). Staff will be offered an incentive of \$50 for completion of the two study visits (baseline and 12 months) and an additional \$25 for the interview, if selected). (4) Maintain communication: For patients, following consent, we will request the names, addresses, and telephone numbers of two friends or relatives, so we can contact patients in the event of a missed appointment. This approach has been a helpful strategy in prior trials. We will implement additional strategies that have led to successful retention of racial/ethnic minority patients in clinical trials such as: provision of a toll-free study telephone number; flexible scheduling; and continuity of study staff to maintain a personal connection to the study. For clinical/nonclinical staff, we will maintain contact through an emailed newsletter for these sites that provides updates about national and statewide health care initiatives but does not discuss intervention-related information. We will also remind staff of the protocol at the monthly meetings.

In addition to these recruitment strategies, a subsample of individuals will be selected to be randomized to one of three Clinical and Translational Science Institute (CTSI) recruitment approaches to complete the eligibility screener and to enroll:

- Proactive outreach by mail or telephone – We will reach out to potential participants proactively by mail and phone. Potential participants will receive two mailings, followed by four telephone calls.
- Proactive outreach through EHR – We will reach out proactively through MyChart to potential participants. Potential participants will receive a message every 2 weeks for a total of four messages.
- Unsolicited text messages – Using an approach we have used previously^{(1) (2)}, we will send unsolicited text messages, using TelASK software, mentioning the study and offering the opportunity to enroll. Texts will be sent by a study team member using a study iPhone. As required by the Federal Communications Commission, these messages will be preceded by a message from the health system, telling

¹ Krebs P, Sherman SE, Wilson H, et al. Text2Connect: a health system approach to engage tobacco users in quitline cessation services via text messaging. *Transl Behav Med.* 2020;10(1):292-301.

² Abrams LC, Wu KC, Krishnan N, et al. A Pilot Randomized Controlled Trial of Text Messaging to Increase Tobacco Treatment Reach in the Emergency Department. *Nicotine Tob Res.* 2021;23(9):1597-1601.

people how to opt out of further messages. If the person does not opt out, they will then receive four text messages over a 2-week period. Text message distribution will be automated using TelASK workflows software where data are timestamped and continuously synchronized with a secure HIPPA compliant server.

- **Interactive Voice Response** – We will reach out to potential participants via phone call with a pre-recorded automated message briefly explaining our research study. Patients will have the option to learn more, leave a call back number for a research assistant or decline participation in the study. Potential participants will receive an automated call every 2 weeks for a total of four calls. These calls will be made using TelASK healthcare services. Participants who respond will be transferred to a research assistant who would then facilitate enrollment.

TelASK is a personalized automated telephone follow-up software that will assist with patient engagement and recruitment for our multiple recruitment strategies. TelASK will work with external vendors such as Lumen (www.lumen.com) for phone calls and Synch (www.synch.com) for SMS text messaging to recruit participants. The only information shared with TelASK will be the participant's name, phone number, and PCP's name. They will assist with the text messaging and interactive voice response (IVR) component of our recruitment strategies.

A convenience sample of individuals who are randomized will be selected to include endorsement from the potential participant's physician. For the letter, EHR message and text message, this would mean it would have signature from the study team and from the person's own physician. For the IVR method, we will include a recorded audio message from a select group of the patient's physicians endorsing the study. All messages would be IRB approved. We will create a stratified recruitment pool that is deliberately balanced with respect to age, sex, race and ethnicity. We will aim to enroll a total of 300 participants using the recruitment strategies mentioned above.

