- Being deemed unable to comply with the study protocol (either self-selected or by indicating during screening that s/he could not complete all requested tasks)
- Participation in other hypertension-related clinical trials
- Have significant psychiatric comorbidity or reports of substance abuse (as documented in the EHR)
- Plan to discontinue care at the practice within the next 15 months

Clinic and nonclinical staff Eligibility Criteria

Inclusion criteria:

- Primary care provider (MD/DO, NP), Nurse, Medical Assistant, or administrative staff employed at the participating practices and interacts with at least five patients with a diagnosis of hypertension.

Exclusion criteria:

- Refuse to participate.

Number of Participants

Implementation Phase

Clinical and nonclinical staff:

Surveys and interviews: 204

Patients:

Surveys: Randomly selected sample of 70 patients from each of the 10 participating primary care clinics (n=700). We will also be selecting a sample of 300 patients across participating clinics who met the eligibility criteria but did not participate in ALTA to participate as a control group.

Interviews: A randomly selected subsample of 30 patients with uncontrolled HTN who participated in ALTA (n=700)

Table of Contents

1 – Introduction	9
1.1 Introductory Statement	9
2 – Background	10
2.1 Background/prevalence of research topic	10
3 – Rationale/Significance	11
3.1 Problem Statement	11
3.2 Purpose of Study/Potential Impact	11
3.3.1 Potential Benefits	12
3.3.2 Potential Risks	13
4 – Study Objectives	15
4.1 Hypothesis	15
4.2 Primary Objective	15
4.3 Secondary Objectives (if applicable)	15
5 – Study Design	16
5.1 General Design	16
5.1.1 Study Duration (if applicable)	17
5.1.2 Number of Study Sites	17
5.2.1 Primary Outcome Variables	17
5.2.2 Secondary and Exploratory Outcome Variables (if applicable)	17
5.3 Study Population	19
5.3.1 Number of Participants	19
5.3.2 Eligibility Criteria/Vulnerable Populations	20
6 – Methods	22
6.1 Description of PF implementation strategy	22
6.1.1 Usual Care (UC) Phase	22
6.1.2 Pre-implementation phase	22
6.1.3 Description of Implementation phase	23
6.1.4 Selection of Instruments/Outcome Measures	24
6.1.5 Intervention Administration	31
6.1.6 Reaction Management	32

6.2.1 Efficacy	32
6.2.2 Safety/Pregnancy-related policy	33
6.2.2.1 Adverse Events Definition and Reporting	33
6.2.3 Pharmacokinetics (if applicable)	33
6.2.4 Biomarkers (if applicable)	33
6.3.1 Study Schedule	33
6.3.2 Informed Consent	34

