Tertiary outcomes will include measures of the patient-provider relationship- relationship commitment, patient-provider trust, patient anxiety in the interaction, patient trust in healthcare, discrimination in medical setting, Health literacy, health intake, and patient trust in medical technology at the pre-intervention (baseline) and post-intervention (12 month) periods.

Relationship commitment: In this study, we operationalize relationship commitment as patients' commitment to maintain care with their PCP when ALTA is introduced into their site. To assess patients' *perceived commitment* to their PCP, we will utilize the self-report measure developed by Berry et al. in a sample of primary care patients. The 5-item measure asks patients to rate their degree of commitment to the relationship with their doctor on a 7-point Likert scale (*strongly disagree* to *strongly agree*). Sample items include: *The relationship with my doctor is...something I am committed to; something I care about; and important to me.* To assess the *behavioral and affective indicators* of relationship commitment we will use natural language processing (NLP) and analyze text of patient-provider interactions that occur in the 12 months prior to ALTA, and over the 12 months ALTA phase. Data will be extracted from the EHR (e.g., clinical notes, messages, and free text) and MyChart to conduct these analyses.

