6.1 Description of PF implementation strategy

6.1.1 Usual Care (UC) Phase

During the UC phase, patients at the sites will receive standard HTN care delivered by their primary care providers. In addition, patients and their providers will receive standard printed HTN treatment guidelines. ALTA will not be implemented at the practices during this period. During this time, bilingual RAs will recruit eligible patients into the study and collect the baseline measures at the patient, staff, and practice-levels.

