6.4.3.3. Tertiary Outcomes

We will use Generalized Linear Mixed Model to analyze the effect of ALTA on differences in relationship commitment (primary outcome) and patient-provider trust (secondary outcome). A Poisson regression model will be used specifying a fixed effect for time, a fixed effect for treatment, a time by treatment interaction, and a control group indicator. Only patients that declined participation in ALTA for the entire evaluation period will be included in the control group for the final analyses. Patients that crossover from the control group to intervention group and continue to participate in the evaluation will be counted towards the intervention group sample. Since they are asked the same questions, it does not impact the analyses. Random effects will be specified for person and clinic to account for the clustered nature of the dataset (observations within person and people within clinics). Relationship commitment will be defined as a continuous variable while patient-provider trust will be categorized as ordinal. Randomization of the stepped wedge design should obviate the need for adjustment, but in the case of imbalance in baseline covariates, these will be included as necessary in adjusted analyses. Sex will be accounted for as a covariate and examined as a potential moderator. All tests will be two-sided with $\alpha=0.05$ for comparison between the ALTA and UC phases.

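### Drawing the survey patients from those already exposed to ALTA conflicts with the planned pre-intervention baseline and, if followed, leaves the survey scales with no usual-care comparison

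*Combined protocol and SAP*

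**What the plan says.** **Sampling frame.** Section 6.3.4 states: "We will still recruit a random sample of 70 patients per clinic that receive care in the 10 safety-net practices", for surveys of the tertiary outcomes. It then mentions the exit-interview subsample and continues: "Patients will be randomly selected from a list of patients who receive care in the clinics and have been exposed to the ALTA project". On order of events it adds: "All patients will provide written informed consent prior to participating in the study".

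**Text that fits this frame.** The Synopsis, in its line on patient interviews, describes the pool of 700 as ALTA participants. Section 5.1.1 puts the consent/baseline visit inside the 12-month implementation phase, and section 6.3.1 describes both patient visits there.

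**Text that does not fit.** Section 6.1.1 says of the UC phase: "ALTA will not be implemented at the practices during this period". It continues: "During this time, bilingual RAs will recruit eligible patients into the study and collect the baseline measures at the patient, staff, and practice-levels". The Synopsis and section 5.2.2 have the tertiary outcomes measured "at the pre-intervention (baseline) and post-intervention (12 month) periods". Section 6.4.3.3 sets two-sided 0.05 tests "for comparison between the ALTA and UC phases" and expects the stepped-wedge randomization to make covariate adjustment unnecessary unless imbalance appears.

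**Controls.** Section 6.3.4 adds 300 eligible patients who ended up not taking part in ALTA. Section 6.4.3.3 keeps in the final control group only those who declined throughout, and moves crossovers to the intervention group.

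**The concern.** A patient can be exposed to ALTA only after the clinic has started it. A sample drawn from exposed patients therefore has its first survey after the intervention began, and that survey is not the pre-intervention value that section 5.2.2 calls for. Any change in commitment or trust that came with referral or first coaching is already in it. The frame also conditions on uptake, because eligible patients whom ALTA never reached cannot be drawn.

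Two kinds of misreporting are at stake. A post-exposure survey could be presented as a baseline, and a contrast between people who took up ALTA and people who refused it could be presented as a randomized phase effect. Tertiary objectives 7 and 8 in section 4.4 (3 and 4 in the Synopsis) depend on these scales in part: the effect of ALTA on the patient-provider relationship, and whether changes in it go with changes in adherence and BP.

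**Working it through.** **1. The plan's own count.** 70 patients × 10 clinics = 700, which agrees with the Synopsis and section 5.3.1. (Section 6.3.4 also mentions approximately 500 patients. The argument does not depend on which total is used.)

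**2. Order of events under section 6.3.4.** Exposure, then selection from the exposed list, then consent, then first survey. ALTA is absent in UC, so nobody on that list can have been selected in UC. UC-phase surveys among patients so drawn: 0 of 700.

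**3. Order of events under section 6.1.1.** Eligible patients are recruited and baselined in UC. UC-phase baselines: up to 700.

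**4. No middle ground.** Section 6.1.2 rules out patient data collection in the pre-implementation phase, so a first survey falls either in UC or after go-live.

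**5. Can the section 6.4.3.3 model estimate the effect under the 6.3.4 frame?** Its fixed terms are time, treatment, time by treatment, and a control-group indicator.
- Treatment coded by phase: with every survey after go-live, treatment = 1 throughout and cannot be separated from the intercept.
- Treatment coded by receipt: treatment = 1 − control indicator, so the two terms are aliased. What can be estimated is participants against decliners, which was not randomized.
- Labelling the first survey as UC does not help, because it codes an exposed measurement as unexposed.

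A numerical check agrees. It used a standard stepped-wedge model for cluster-period means with 5 sequences of 2 sites and 6 periods (the five cohorts of Figure 1; 5 × 2 = 10 sites). With the UC cells present, the treatment effect has a standard error. With them deleted, the information matrix is rank-deficient and none exists. The number of sequences does not matter here, since treatment is constant once the UC cells are gone.

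**6. Do the 300 controls fill the gap?** No. They are defined by not participating or by declining, and declining presupposes an offer. They are not a UC-phase sample.

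**7. Which outcomes are touched?** Only the patient survey scales. Sections 5.2.2 and 6.1.4 give the text-derived measures a window of 12 months before ALTA and the 12-month ALTA phase. BP and PDC come from the EHR.

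**The case against.** The strongest reply is that section 6.1.1 plans patient recruitment and baseline collection in UC, and that the Synopsis and section 5.2.2 call the baseline pre-intervention. On that reading the exposed-patient sentence is a stray. It directly follows the sentence on selecting 30 exit interviewees, for whom exposure is a sensible requirement. Exposure is not defined, and none of the five recruitment methods in section 6.3.4 requires it.

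Part of this stands. A reader might infer that no UC-phase survey exists. The documents do not support that: they contain two incompatible rules and do not say which was followed. But the stray-sentence reading is weak. The next sentence sets the 300 non-participants against this sample, and the Synopsis and sections 5.1.1 and 6.3.1 fit the exposed frame.

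A reader might also infer that every intervention patient is first surveyed after their own ALTA contact. That fails because section 5.3.2 expects controls to cross over and section 6.4.3.3 counts them as intervention patients. Such patients can have a survey before they participate. They do not thereby supply a UC-phase survey, and any within-person contrast they give is self-selected.

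Two further inferences go beyond the documents. The share of an effect lost to a late baseline depends on how much had accrued by the first survey, and nothing in the plan gives that. Nor can one say how far the last survey falls beyond the facilitated period: section 6.3.6 times that visit from randomization, and section 5.1 adds a 3-month site-level period for outcome assessment.

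Finally, these are tertiary outcomes, and the fidelity, BP and PDC analyses are untouched. That limits the reach of the problem but does not remove it.

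**Conclusion.** The contradiction is real and the text is wrong as it stands. Following section 6.3.4 gives 0 of 700 UC-phase surveys among the patients drawn and no estimable ALTA-versus-UC effect on the patient commitment and trust scales. Following section 6.1.1 gives up to 700 and an estimable effect. The first result assumes that the exposed-patient sentence governs the survey sample, which is its more natural reading, and that the controls are surveyed after go-live.

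It would be too strong to say that the two relationship objectives cannot be answered at all. They are compromised only for their survey measures. The direction of the baseline problem is clear, since any effect that precedes the first survey is removed from the measured change, but its size cannot be given from the documents.

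**What to change.** 1. **Reconcile the text.** Make sections 6.3.4, 5.1.1 and 6.3.1 agree with sections 6.1.1, 5.2.2 and 6.4.3.3 on who is sampled, when the first survey is taken relative to go-live, and which data form the UC comparator.
2. **Where a clinic has not yet gone live,** draw its 70 patients during UC from the EHR list of eligible patients, survey them then, and follow them whether or not ALTA later reaches them. The documents do not show that any clinic is still in UC, so this step may apply to few or none.
3. **For every surveyed patient, crossovers included,** take the date of first ALTA referral or coaching from the EHR time stamps. Accept the first survey as a pre-intervention baseline only if it came before that date.
4. **Limit the claims.** Restrict pre-post survey results to those patients. Report the others as a non-randomized post-exposure comparison with the 300 controls, with no claim of a randomized ALTA-versus-UC effect. In section 6.4.3.3, do not rely on the stepped-wedge randomization for that comparison.
5. **State the fallback.** If few or no patients have a survey before first contact, say that the survey scales cannot estimate change due to ALTA.

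The cost is a few sentences and one date variable from system files that sections 6.1.4 and 6.4.3.1 already have extracted quarterly. The drawbacks are that a UC-drawn sample will include patients who never receive ALTA, and that the pre-post survey set may be small or empty.
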